6.2 Usage of Concurrent/Concomitant Medications

Clinical discretion may be used in managing radiotherapy-related and androgen deprivation-related side effects.

Bowel: Patients will be asked to adhere to a low gas, low motility diet commencing one day prior to treatment. Patients experiencing diarrhea/rectal frequency/urgency may be managed initially with psyllium fiber supplements can be used to help increase bulkiness of bowel movements. If diarrhea persists, they may then be managed with diphenoxylate or loperamide.

Urinary: Bladder irritation may be mitigated with phenazopyridine. Urinary frequency/urgency can be managed with anticholinergic agents or alpha-blockers such as tamsulosin.

Erectile Dysfunction: Erectile dysfunction can be managed with phosphodiesterase (PDE) inhibitors such as sildenafil.

Abnormal liver function tests: If liver transaminases (AST) or (ALT) are >2x the upper limit of normal, the anti-androgen may be discontinued.

Hot flashes: Frequent and bothersome hot flashes can be managed with a serotonin-norepinephrine reuptake inhibitor, venlafaxine.

Bone Health: Osteopenia and minimization of risk of osteoporosis can be managed with Calcium + Vitamin D supplementation.

7 Reporting and Documentation of Results

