5.1.1 Anti-Androgen Therapy: Enzalutamide

Timing: Enzalutamide therapy will begin within 0-7 days (can begin before or same day as, or after) of the date of the first LHRH agonist administration and continue for a total duration of 24 months. The total duration of administered anti-androgen therapy must be documented and submitted.

Description: Enzalutamide is a nonsteroidal androgen receptor antagonist developed by the pharmaceutical company Medivation/Astellas. The chemical name is 4-(3-(4-Cyano-3-(trifluoromethyl)phenyl)-5,5-dimethyl-4-oxo-2-thioxoimidazolidin-1-yl)-2-fluoro-N-methylbenzamide. Enzalutamide has approximately 9-fold greater binding affinity to the androgen receptor compared to the antiandrogen bicalutamide. As opposed to

Version date: 09-05-2017

Protocol CC#: 15558

bicalutamide, enzalutamide does not promote translocation of the androgen receptor to the nucleus and in addition prevents binding of the androgen receptor to DNA and to coactivator proteins. In two clinical trials in patients with metastatic castration-resistant prostate cancer pre- and post-docetaxel (PREVAIL and AFFIRM, respectively), enzalutamide demonstrated improvements in overall survival and was well-tolerated.

Supply: From Medivation/Astellas through NCCN's vendor CRMG

Storage: Enzalutamide should be stored in a dry place at room temperature between 68°-77°F.

Administration: Enzalutamide is administered orally at a dose of 160 mg (for 40 mg capsules) per day. Enzalutamide can be taken with or without food. Swallow capsules whole. Do not chew, dissolve, or open the capsules.

Administration will be suspended only if there is an apparent or suspected reaction to the drug. During RT interruptions, enzalutamide will be continued. Any treatment interruptions or failure of the patient to comply with the prescribed medication schedule must be documented.

Toxicity: Consult the package insert for comprehensive toxicity information (Table 5).

Table 5: Adverse Reactions

| | ENZALUTAMIDE (N=800) | | PLACEBO (N=399) | |
|--|----------------------|---------------------|---------------------|---------------------|
| General Disorders | Grade 1-4(%) | Grade 3-4(%) | Grade 1-4(%) | Grade 3-4(%) |
| Asthenic Conditions | 50.6 | 9.0 | 44.4 | 9.3 |
| Peripheral Edema | 15.4 | 1.0 | 13.3 | 0.8 |
| Musculoskeletal and Connective Tissue Disorders | | | | |
| Back Pain | 26.4 | 5.3 | 24.3 | 4.0 |
| Arthralgia | 20.5 | 2.5 | 17.3 | 1.8 |

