| Musculoskeletal Pain | 15.0 | 1.3 | 11.5 | 0.3 |
| Muscular Weakness | 9.8 | 1.5 | 6.8 | 1.8 |
| Musculoskeletal Stiffness | 2.6 | 0.3 | 0.3 | 0.0 |
| Gastrointestinal Disorders | | | | |
| Diarrhea | 21.8 | 1.1 | 17.5 | 0.3 |
| Vascular Disorders | | | | |
| Hot Flush | 20.3 | 0.0 | 10.3 | 0.0 |
| Hypertension | 6.4 | 2.1 | 2.8 | 1.3 |
| Nervous System Disorders | | | | |
| Headache | 12.1 | 0.9 | 5.5 | 0.0 |
| Dizziness | 9.5 | 0.5 | 7.5 | 0.5 |
| Spinal Cord Compression and Cauda Equina Syndrome | 7.4 | 6.6 | 4.5 | 3.8 |
| Paresthesia | 6.6 | 0.0 | 4.5 | 0.0 |
| Mental Impairment Disorders ^d | 4.3 | 0.3 | 1.8 | 0.0 |

| | | | | |
|---|------|-----|-----|-----|
| Hypoesthesia | 4.0 | 0.3 | 1.8 | 0.0 |
| Infections and Infestations | | | | |
| Upper Respiratory Tract Infection ^e | 10.9 | 0.0 | 6.5 | 0.3 |
| Lower Respiratory Tract and Lung Infection ^f | 8.5 | 2.4 | 4.8 | 1.3 |
| Psychiatric Disorders | | | | |
| Insomnia | 8.8 | 0.0 | 6.0 | 0.3 |
| Anxiety | 6.5 | 0.3 | 4.0 | 0.0 |
| Renal and Urinary Disorders | | | | |
| Hematuria | 6.9 | 1.8 | 4.5 | 1.0 |
| Pollakiuria | 4.8 | 0.0 | 2.5 | 0.0 |
| Injury, Poisoning, and Procedural Complications | | | | |
| Fall | 4.6 | 0.3 | 1.3 | 0.0 |
| Non-pathologic Fractures | 4.0 | 1.4 | 0.8 | 0.3 |
| Skin and Subcutaneous Tissue Disorders | | | | |
| Pruritis | 3.8 | 0.0 | 1.3 | 0.0 |
| Dry Skin | 3.5 | 0.0 | 1.3 | 0.0 |
| Respiratory Disorders | | | | |
| Epistaxis | 3.3 | 0.1 | 1.3 | 0.3 |

The safety and tolerability of enzalutamide as monotherapy have been evaluated in a combined safety analysis including metastatic castration resistant prostate cancer patients from 2 large randomized, placebo-controlled phase 3 studies (PREVAIL and AFFIRM). Overall enzalutamide was generally well tolerated. In these studies, adverse events included fatigue, constipation, diarrhea, hot flush, asthenia, headache, insomnia, hypertension.

Dose Modifications: If a patient experiences a \geq Grade 3 toxicity or an intolerable side effect, withhold dosing for one week and until symptoms improve to \leq Grade 2, then resume at the same or a reduced dose (120 mg or 80 mg), if warranted.

Drug-Drug Interactions: The concomitant use of strong CYP2C8 inhibitors should be avoided if possible. If patients must be co-administered a strong CYP2C8 inhibitor,

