6.1.5 Discontinuation of Therapy

If a patient experiences a \geq Grade 3 toxicity or an intolerable side effect, withhold dosing for one week and until symptoms improve to \leq Grade 2, then resume at the same or a reduced dose (120 mg or 80 mg), if warranted.

In addition, the following safety/compliance events will result in the removal of patients from therapy either permanently or until the etiology of the problem has been identified and resolved:

- Any adverse event that is intolerable to the patient and that cannot be ameliorated by the use of adequate medical intervention, or that in the opinion of the investigator would lead to undue risk to the patient if dosing continued.
- Any seizure
- Creatinine >4.0 mg/dL
- Liver function tests (AST, ALT, or total bilirubin) >2 times the upper limit of normal
- An absolute neutrophil count $\leq 750/\mu\text{L}$
- A platelet count of $<50,000/\mu\text{L}$
- Patients who are in the opinion of the investigator or the medical monitor non-compliant with the protocol's requirements

The Investigator will withdraw a patient whenever continued participation is no longer in the patient's best interests. Reasons for withdrawing a patient include, but are not limited to, disease progression, the occurrence of an adverse event or a concurrent illness, a patient's request to end participation, a patient's non-compliance or simply significant uncertainty on the part of the Investigator that continued participation is prudent. There may also be administrative reasons to terminate participation, such as concern about a patient's compliance with the prescribed treatment regimen.

Table 6: Schedule of Assessments

| Study Assessments | Pre-Radiation Treatment | | During Radiation | Post-Radiation Treatment |
|--|-------------------------|--|---|--|
| | Baseline (Diagnosis) | 4-6 week after initiation of ADT (at placement of fiducial marker) | At Time of Brachytherapy Procedure (After fractionated whole pelvic radiotherapy) | Each follow up visit (6 wk, month 3-4, month 6, month 12, month 18, month 24, and month 36) ^a |
| Detailed medical history and physical exam | X | | | X (pertinent interval history and physical exam) |
| Collection of archival biopsy tissue if available | X | | | |
| TRUS biopsy of dominant lesion(s) ^b | X | X | X | |
| Serum PSA, testosterone | X | X | X | X |
| CBC with differential | X | X | X | X |
| Basic Metabolic Panel | X | X | X | X |

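### At the same AST/ALT threshold, removal from therapy is obligatory in section 6.1.5 and discretionary in section 6.2; the suspension sentence in section 5.1.1 also conflicts with other stopping rules

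*Combined protocol and SAP*

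**What the plan says.** Four places in the protocol govern interruption or stopping of enzalutamide. Section numbers are those in the body of the protocol. Two subsections are numbered 5.1.1, and the one meant here is the enzalutamide subsection.

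- **6.1.5, Discontinuation of Therapy.** Listed safety and compliance events "will result in the removal of patients from therapy either permanently or until the etiology of the problem has been identified and resolved". One of them is "Liver function tests (AST, ALT, or total bilirubin) >2 times the upper limit of normal". Others are a creatinine limit, neutrophil and platelet limits, any seizure, and non-compliance.
- **6.2, Usage of Concurrent/Concomitant Medications.** The section opens with "Clinical discretion may be used in managing radiotherapy-related and androgen deprivation-related side effects" and later states that, for AST or ALT above 2x ULN, "the anti-androgen may be discontinued".
- **5.1.1, Anti-Androgen Therapy: Enzalutamide.** The Administration paragraph states: "Administration will be suspended only if there is an apparent or suspected reaction to the drug". It adds that the drug continues through radiotherapy interruptions. The Dose Modifications paragraph of the same subsection, repeated in 6.1.5, says that for a toxicity of grade 3 or worse "or an intolerable side effect, withhold dosing for one week and until symptoms improve to" grade 2 or lower.
- **3.5, Duration of Therapy.** Treatment may end for disease progression, intercurrent illness, non-compliance and other reasons, several of which are not drug reactions.

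**The concern.** The same laboratory result is given two instructions of different force. An investigator who reads 6.1.5 must take the patient off therapy, at least for a time. One who reads 6.2 may leave the patient on drug. Both can cite the protocol. The situation is foreseeable: eligibility requires AST or ALT below twice the upper limit (3.2.1), and Table 6 schedules liver tests at every assessment column. A crossing would therefore normally be a new on-study event that staff must act on. The protocol also provides for participating sites (10.6, Appendix 2), so different readings are a practical possibility.

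The sentence in 5.1.1 raises a second, lesser problem. Read literally, it makes a suspected drug reaction the sole ground for suspension, although other sections give further grounds.

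What is at stake is mainly the consistency of safety instructions. Safety and feasibility of the combination form the first primary objective (2.1).

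**Working it through.** No figure in the plan needs reproducing for the main point, which is a comparison of texts.

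**Step 1. The liver rule.**

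| | 6.1.5 | 6.2 |
|---|---|---|
| Threshold | above 2x ULN | above 2x ULN |
| Tests | AST, ALT, total bilirubin | AST, ALT |
| Force | obligatory (*will*) | discretionary (*may*) |
| Action | removal, permanent or until the cause is found and resolved | discontinuation |
| Applies to | therapy, with no statement on whether leuprolide is included | the anti-androgen |
| Cross-reference or precedence | none | none |

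For AST or ALT the threshold is identical. Under 6.1.5 the least permitted action is a temporary removal. Under 6.2 no action is required. The two cannot both be the rule, whatever view is taken of permanent stopping.

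**Step 2. The 5.1.1 sentence against the other triggers.** Let R mean that a reaction to the drug is apparent or suspected. The Administration paragraph permits suspension only if R holds.

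- *6.1.5 laboratory limits (creatinine, neutrophils, platelets) and non-compliance:* removal is required with no condition on R. When R is false the two sections conflict. Non-compliance is the plainest case, since it is not a drug reaction.
- *3.5:* intercurrent illness, progression and non-compliance can end treatment without R.
- *Grade 3 or higher withholding (5.1.1 Dose Modifications and 6.1.5):* no attribution condition is stated. If the toxicity is judged not drug-related, for example a radiation toxicity, the Administration paragraph says not to suspend and the Dose Modifications paragraph says to withhold.
- *Liver tests:* a rise may itself be a suspected reaction. In that case R is true, and 5.1.1 and 6.1.5 agree.

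**Step 3. How many patients.**

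- Liver limb: the documents give no rate of AST or ALT above 2x ULN, so no count can be formed.
- Grade 3 limb: the inputs are the usual rate of grade 3 or higher toxicity, 12% (9.2.1), and 53 patients. 0.12 x 53 = 6.36, about 6.

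That 6 is the expected number with any grade 3 or higher event at the assumed rate. The instructions conflict only for the subset whose event is judged not even possibly drug-related and occurs while enzalutamide is being taken. The 12% covers acute or late toxicity. Toxicity is followed to 36 months after radiotherapy (2.4.1), whereas enzalutamide lasts 24 months, so some events may fall after dosing ends. The documents do not allow the subset to be sized.

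**The case against.** The best defence is that the sections can be read together. Section 6.1.5 carries the discontinuation title and allows a temporary removal, while 6.2 is a supportive-care list that might leave only full discontinuation to judgement. The sentence in 5.1.1 stands next to the instruction to continue through radiotherapy breaks, so it may be meant only to prevent pauses for that reason. The Dose Modifications paragraph follows the drug's adverse-reaction table, so toxicity there may mean drug toxicity, and a suspected reaction is a low bar. Suspension might also mean only a temporary pause, which would leave the reasons in 3.5 for ending treatment untouched.

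Much of this narrows the point, but none of it removes it. Section 6.2 does not say that it concerns only permanent stopping or that it yields to 6.1.5. Even on the harmonised reading, 6.2 mentions no obligatory hold. The attribution condition that would reconcile the grade 3 rule with the 5.1.1 sentence is not written, and no reading of a suspected reaction covers non-compliance. If suspension means a temporary pause, the temporary removals in 6.1.5 are still suspensions.

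A reader might infer four stronger points, which the documents do not support:

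- *That 6.1.5 demands permanent stopping where 6.2 makes it optional.* The clause in 6.1.5 allows temporary removal.
- *That the absence of bilirubin from 6.2 is a further contradiction.* Section 6.2 is silent on bilirubin, and 6.1.5 covers it.
- *That about 6 of 53 patients would receive opposite instructions.* That figure counts everyone expected to have a grade 3 or higher event, not those for whom the rules diverge.
- *That a planned result is distorted.* The primary endpoints are toxicity rates and PSA complete response (2.4.1). Section 9.4 plans no analysis of exposure or discontinuation, analyses include all patients, and follow-up continues after treatment stops (3.3).

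**Conclusion.** The contradiction over AST/ALT above 2x ULN is real and rests on the text alone: 6.1.5 obliges at least a temporary removal, 6.2 does not, and nothing sets precedence. The 5.1.1 sentence is a secondary conflict. It is clear against non-compliance and intercurrent illness, and against the laboratory limits and the grade 3 withholding rule whenever the event is judged unrelated to the drug.

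The size cannot be derived from the documents. For the grade 3 limb, about 6 of 53 is at most an upper bound. It assumes that the plan's 12% holds for all grade 3 or higher toxicity, and it does not count intolerable lower-grade effects, which trigger the same rule. No effect on a planned analysis is shown. This should be corrected because it concerns safety instructions and costs little; it does not undermine the design.

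**What to change.** Reconcile 3.5, 5.1.1, 6.1.5 and 6.2 into one consistent set of interruption and discontinuation rules, preferably a single table to which the other sections refer. For each trigger, state:

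- whether action is mandatory or discretionary;
- whether it is temporary or permanent;
- whether attribution to the drug matters, using the attribution scale already in 7.4;
- which drug or drugs the action covers.

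Reword or remove the 5.1.1 suspension sentence so that it agrees with that table. Which clinical rule applies at each trigger is for the sponsor to decide. The cost is an amendment to protocol wording, with no additional patients or data.

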7.1 Definitions

Evaluable for toxicity

All patients will be evaluable for toxicity from the time of their first treatment with the study drug until 24 months after last dose of enzalutamide treatment.

7.2 Evaluation of Safety

Analyses will be performed for all patients. The study will use the [CTCAE v4.0](#) for reporting of adverse events.

Safety will be assessed through a summary of adverse events. The maximum severity of each adverse event assessed by NCI CTCAE v. 4.0 will be summarized using summary statistics, graphical techniques, and categorical methods. Shift tables using CTCAE grades will be used to compare baseline to on-treatment values.

7.3 Definitions of Adverse Events

7.3.1 Serious Adverse Event

The term "Serious Adverse Event" (or "SAE") shall mean any adverse drug experience occurring at any dose that results in any of the following outcomes: death, is life threatening, as defined below, requires inpatient hospitalization or prolongation of an existing hospitalization, results in a persistent or significant disability or incapacity, results in a congenital anomaly or birth defect, results in cancer, or results in an

important medical event. Important medical events which are AEs that may not result in death, be Life-Threatening, or require hospitalization may be considered SAEs when, based upon appropriate medical judgment, they may jeopardize the Study Participant and may require medical or surgical intervention to prevent one of the outcomes listed in this definition. Examples of such medical events include allergic bronchospasm requiring intensive treatment in an emergency room or at home, blood dyscrasias or convulsions that do not result in inpatient hospitalization, or the development of drug dependency or drug abuse.

All SAES must be reported to ORP [REDACTED].

7.3.2 Adverse reaction

An adverse reaction is defined as any adverse event caused by the use of a treatment or procedure. Adverse reactions are a subset of all suspected adverse reactions for which there is reason to conclude that the treatment or procedure caused the event. Adverse events will be followed up to 60 months post-initiation of androgen deprivation therapy.

7.3.2.1 Suspected

A suspected adverse reaction is defined as any adverse event for which there is a reasonable possibility that the treatment or procedure caused the adverse event. For the purposes of IND safety reporting, “reasonable possibility” indicates that there is evidence to suggest a causal relationship between the treatment or procedure and the adverse event. A suspected adverse reaction implies a lesser degree of certainty about causality than an adverse reaction.

7.3.2.2 Unexpected

An adverse event or suspected adverse reaction is considered *unexpected* if it is not listed in the investigator brochure or package insert(s), or is not listed at the specificity or severity that has been observed, or, if an investigator brochure is not required or available, is not consistent with the risk information described in the general investigational plan or elsewhere in the current application.

“Unexpected,” as used in this definition, also refers to adverse events or suspected adverse reactions that are mentioned in the investigator brochure as occurring with a class of treatment or procedure or as anticipated from the pharmacological properties of the treatment or procedure, but are not specifically mentioned as occurring with the particular treatment or procedure under investigation.

Adverse events that would be anticipated to occur as part of the disease process are considered *unexpected* for the purposes of reporting because they would not be listed in the investigator brochure. For example, a certain number of non-acute deaths in a cancer trial would be anticipated as an outcome of the underlying disease, but such deaths would generally not be listed as a suspected adverse reaction in the investigator brochure.

Some adverse events are listed in the Investigator’s Brochure as occurring with the same class of treatment, or as anticipated from the pharmacological properties of the drug, even though they have not been observed with the drug under investigation. Such events would be considered *unexpected* until they have been observed with the drug

under investigation. For example, although angioedema is anticipated to occur in some patients exposed to drugs in the ACE inhibitor class and angioedema would be described in the investigator brochure as a class effect, the first case of angioedema observed with the drug under investigation should be considered *unexpected* for reporting purposes.

7.3.2.3 Life-threatening

An adverse event or suspected adverse reaction is considered *life-threatening* if, in the view of either the investigator or sponsor, its occurrence places the patient or subject at immediate risk of death. It does not include an adverse event or suspected adverse reaction that, had it occurred in a more severe form, might have caused death.

7.4 Recording of an Adverse Event

All grade 3 and above adverse events will be entered into OnCore[®], whether or not the event is believed to be associated with use of the study drug. Data about these events and their severity will be recorded using the NCI CTCAE v4.0.

The Investigator will assign attribution of the possible association of the event with use of the investigational drug, and this information will be entered into OnCore[®] using the classification system listed below:

| Relationship | Attribution | Description |
|--|-------------|--|
| Unrelated to investigational drug/intervention | Unrelated | The AE is clearly NOT related to the intervention |
| | Unlikely | The AE is doubtfully related to the intervention |
| Related to investigational drug/intervention | Possible | The AE may be related to the intervention |
| | Probable | The AE is likely related to the intervention |
| | Definite | The AE is clearly related to the intervention |

Signs or symptoms reported as adverse events will be graded and recorded by the Investigator according to the CTCAE. When specific adverse events are not listed in the CTCAE they will be graded by the Investigator as *none, mild, moderate* or *severe* according to the following grades and definitions:

| | |
|----------|---|
| Grade 0 | No AE (or within normal limits) |
| Grade 1 | Mild; asymptomatic or mild symptoms; clinical or diagnostic observations only; intervention not indicated |
| Grade 2 | Moderate; minimal, local, or noninvasive intervention (e.g., packing, cautery) indicated; limiting age-appropriate instrumental activities of daily living (ADL) |
| Grade 3: | Severe or medically significant but not immediately life-threatening; hospitalization or prolongation of hospitalization indicated; disabling; limiting self-care ADL |
| Grade 4: | Life-threatening consequences; urgent intervention indicated |
| Grade 5: | Death related to AE |

